7.1.1. Phase 1 – Dose Escalation

Multiple dose levels of TP-0184, with approximately 1 to 6 patients at each level will be evaluated. There must be at least 3 DLT evaluable patients at a specific dose level if there is a DLT observed in that level. The first dose cohort will start at 20 mg/day every day. Patients will receive their first dose of TP-0184 starting on Cycle 1 Day 1. Dose escalation is planned to proceed with patients receiving each provisional dose level of 40 mg, 60 mg, 90 mg, 120 mg, 160 mg, 210 mg, and 270 mg. Additional dose increments of up to 25% from one dose cohort to the next may occur. In order to determine the recommended Phase 2 dose, dose escalation may continue until one of the following occurs:

1. An MTD is determined.
2. An MAD is determined based on the totality of safety data and medical considerations by the SRC and sponsor.

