7.3.2. Description of Dose Escalation Study

7.3.1. Phase 1 Dose Escalation

Dose escalation will be performed using a design based on a 2-parameter BLRM ([Neuenschwander 2008](#)). The BLRM method will be applied along with the escalation with overdose control (EWOC) principle to control the risk of exposing patients to toxic doses ([Babb 2013](#)). Based on this principle, a dose level will be considered safe if the probability of excessive toxicity (ie, the probability of a DLT rate over 33% is no greater than 25%). The MTD with estimated posterior probability of a DLT within target toxicity interval (16%, 33%) among the admissible doses fulfilling EWOC is determined by BLRM. The MTD is estimated based on observed DLTs.

The use of Bayesian adaptive models for Phase 1 studies has been advocated by the European Medicines Agency's guideline on clinical trials in small populations ([European Medicines Agency, 2016](#)).

The actual dose level to be tested in the next cohort will be chosen based on the above risk assessment, using the BLRM method. The dose recommended by the BLRM method will be treated as guidance and will be integrated with a clinical assessment of the safety adverse event information and review of clinical data, including above safety and PK data. Intermediate doses between planned dose levels may be SDP Oncology explored based on safety consideration after discussion and concurrence with SRC members and SDP Oncology clinical team. The BLRM method estimates the MTD by updating the probability of observing a DLT for each dose level in the study as DLT information becomes available. An additional cohort with a different dose schedule may be considered based on clinical judgment supported by medical observations.

Procedures for close monitoring of the DLT period and entire study have been established ([Section 12.1](#), [Section 14.1](#)). In addition, an SRC will conduct scheduled meetings and will provide safety oversight of the patients, determine DLTs, and guide escalation and dose decisions ([Section 7.3.3](#)).

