20.1.1.2. Prior Specifications

The bivariate normal prior for the BLRM parameters with a reference dose level of 90 mg is obtained as follows:

The following noninformative prior for $(\log(\alpha), \log(\beta))$ was used:

- The mean of $\log(\alpha)$ was set to -0.847 and mean of $\log(\beta)$ was set to 0.913 to allow the median DLT rate to be around 1%.
- The standard deviation of $\log(\alpha)$ was set to 1.275, and the standard deviation of $\log(\beta)$ to 0.482, which allows for considerable prior uncertainty for the dose-toxicity profile.
- The correlation between $\log(\alpha)$ and $\log(\beta)$ was set to -0.9.

Table 11 Prior Parameters for Bivariate Normal Distribution of Model Parameters

Parameters	Means	Standard Deviations	Correlation
$\log(\alpha), \log(\beta)$	(-0.847, 0.913)	(1.275, 0.482)	-0.9

Table 12 Prior Distribution Summaries Derived from Priors in Table 11

TP-0184 Dose (mg)	Prior Probabilities Pr(DLT) is in Interval:			Mean	SD	Quantiles		
	(0, 0.16]	(0.16, 0.33]	(0.33, 1]			2.5%	50%	97.5%
20	0.8685	0.0744	0.0571	0.06784	0.13677	0	0.0101	0.5253
40	0.7191	0.1414	0.1395	0.13674	0.18611	0.00026	0.05436	0.6946
60	0.5463	0.2089	0.2448	0.21414	0.21583	0.00324	0.1354	0.77793
90	0.2602	0.282	0.4578	0.34556	0.22766	0.03638	0.3026	0.84387
120	0.0303	0.2178	0.7519	0.48932	0.20034	0.15282	0.47701	0.87993
160	0	0.0119	0.9881	0.66399	0.14196	0.37032	0.67276	0.91269
210	0	1e-04	0.9999	0.80101	0.09715	0.57776	0.81558	0.95098
270	0	0	1	0.88234	0.06829	0.72003	0.89404	0.98476

Note: Bold doses indicate not meeting the overdose control criterion (more than 25% chance of over-dosing) with the prior information only.

Abbreviation: DLT = dose-limiting toxicity.

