20.1.1.3. Dose Recommended by the BLRM Method

The dose allocation will start at the dose of 20 mg. Patients will be included by cohort of 1 to 6 patients. There must be at least 3 DLT evaluable patients at a specific dose level if there is a DLT observed in that level. After each cohort of patients is completed, the dose recommendation by the model will be based on posterior summaries including the mean, median, standard deviation, 95% credible interval, and the probability that the true DLT rate for each dose lies in one of the following categories:

- (0, 16%]: under-dosing
- (16%, 33%]: targeted toxicity
- (33%, 100%]: over-dosing

Following the principle of EWOC, after each cohort of patients the recommended dose by the model is the one with the highest posterior probability of the DLT rate falling in the targeted toxicity interval (16%, 33%] among the admissible doses fulfilling EWOC, i.e., it is unlikely (< 25% posterior probability) that the DLT rate at the dose falls in the over-dosing interval.

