In general, when no DLTs are observed in 3 patients at a dose level, the decision is to increase the dose. When 1 DLT is observed in 3 patients, the decision is to stay at the current dose level or to escalate to the higher provisional dose level. When more than 1 DLT is observed in a 3-patient cohort, the decision is to decrease the dose level or to stay at the current level.

**APPENDIX 3. REVISED INTERNATIONAL PROGNOSTIC SCORING
SYSTEM (IPSS-R)**

IPSS-R Cytogenetic Risk Groups*, **

Cytogenetic prognostic subgroups	Cytogenetic abnormalities:
Very good	-Y, del(11q)
Good	Normal, del(5q), del(12p), del(20q), double including del(5q)
Intermediate	del(7q), +8, +19, +17q, any other single or double independent clones
Poor	-7, inv(3)/t(3q)/del(3q), double including -7/del(7q), Complex: 3 abnormalities
Very poor	Complex >3 abnormalities

IPSS-R Prognostic Score Values*

Prognostic variable	0	0.5	1	1.5	2	3	4
Cytogenetics	Very Good	-	Good	-	Intermediate	Poor	Very Poor
BM Blasts (%)	≤2	-	>2 - <5	-	5 - 10	>10	-
Hemoglobin (g/dL)	≥10	-	8 - <10	<8	-	-	-
Platelets (x10 ⁹ /L)	≥100	50 - <100	<50	-	-	-	-
ANC (x10 ⁹ /L)	≥0.8	<0.8	-	-	-	-	-

IPSS-R Prognostic Risk Categories/Scores*

Risk Category	Risk Score
Very Low	≤1.5
Low	>1.5 - 3
Intermediate	>3 - 4.5
High	>4.5 - 6
Very High	>6

IPSS-R: Prognostic Risk Category Clinical Outcomes*

	No. pts	Very Low	Low	Intermediate	High	Very High
Subjects (%)	7012	19%	38%	20%	13%	10%
Survival***	-	8.8	5.3	3.0	1.6	0.8
AML/25%**^	-	NR	10.8	3.2	1.4	0.7

**Median, year.

^Median time to 25% AML evolution.

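### Appendix 2 offers escalation after 1 DLT in 3 patients, which the 25% overdose limit bars in ordinary first cohorts, and omits the de-escalation that Table 15 shows

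*Protocol*

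**What the plan says.** Protocol Appendix 2, Section 20.1.1.3, gives the allocation rule: "the recommended dose by the model is the one with the highest posterior probability of the DLT rate falling in the targeted toxicity interval", taken over the doses that pass overdose control. A dose passes if "it is unlikely (< 25% posterior probability) that the DLT rate at the dose falls in the over-dosing interval", which is a DLT rate above 33%. Section 7.3.1 (Phase 1 Dose Escalation) states the same control: "the probability of a DLT rate over 33% is no greater than 25" percent.

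Table 15 applies this rule to example histories. The paragraph that closes Appendix 2, after Section 17.2.5, then summarises the behaviour in words:

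- 0 DLTs in 3: "when no DLTs are observed in 3 patients at a dose level, the decision is to increase the dose".
- 1 DLT in 3: "When 1 DLT is observed in 3 patients, the decision is to stay at the current dose level or to escalate", where escalation means going up one provisional level.
- More than 1 DLT in a 3-patient cohort: decrease or stay.

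Section 7.1.1 plans cohorts "with approximately 1 to 6 patients at each level will be evaluated".

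**The concern.** Nowhere else does the protocol translate DLT counts into actions in plain language, so a committee member is likely to remember this paragraph. For 1 DLT in 3 it permits going up and does not mention going down. An observed rate of one in three sits at the edge of the over-dosing interval. It would be surprising if a model with a 25% limit on the chance of exceeding 33% let the dose rise on that evidence. If the model does not, the summary errs in the unsafe direction and contradicts both the rule and the table it summarises.

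**Working it through.** **1. Table 15 as printed (no modelling).** There is no 1/3 row. The rows with one DLT are:

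| Scenario | DLTs at last dose | Next dose | Action |
|---|---|---|---|
| 4 | 1/4 at 90 mg | 90 mg | stay |
| 5, 6 | 1/4 at 120 mg | 90 mg | down |
| 7 | 1/4 at 160 mg | 120 mg | down |
| 8, 9 | 1/6 at 160 mg | 120 mg | down |

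None escalates. Five of the six rows take an action that the paragraph does not list for one DLT. (Scenario 9 repeats scenario 8, so this is four of five distinct rows.) With the same history below, 1/3 is worse evidence than 1/4 or 1/6, so a 1/3 row could not look more favourable.

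**2. Model.** logit π(d) = log α + β·log(d/90), from Appendix 2. The prior is from Table 11: (log α, log β) bivariate normal, means −0.847 and 0.913, SDs 1.275 and 0.482, correlation −0.9. The likelihood is binomial at each dose, and the posterior was obtained by integration over a grid. Write P for the posterior probability that π(d) > 0.33. A dose is admissible if P < 0.25. The recommendation is the admissible planned dose with the highest probability of 0.16 < π(d) ≤ 0.33.

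**3. Reproducing the plan's figures.** The grid matches the over-dosing column of Table 12 within 0.005. Against the P(overtox) column of Table 15:

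| Scenario | Printed | Grid |
|---|---|---|
| 1 | 0.1462 | 0.145 |
| 2 | 0.2312 | 0.26 |
| 3 | 0.1501 | 0.15 |
| 4 | 0.1293 | 0.15 |
| 5 | 0.0269 | 0.03 |
| 6 | 0.0194 | 0.02 |
| 7 | 0.1222 | 0.12 |
| 8 | 0.0503 | 0.05 |

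The next dose agrees except in scenario 2. There the grid value crosses 0.25, so the recomputed model goes to 60 mg where the table prints 90 mg. That gap, about 0.03, is the largest.

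**4. First cohort of 1/3, with 0/3 at each lower level.**

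| Current dose | P at current dose | P at next planned dose | Recommendation |
|---|---|---|---|
| 20 mg | 0.20 | 0.51 (40 mg) | stay |
| 40 mg | 0.14 | 0.38 (60 mg) | stay |
| 60 mg | 0.12 | 0.50 (90 mg) | stay |
| 90 mg | 0.20 | 0.69 (120 mg) | stay |
| 120 mg | 0.40 | 0.98 (160 mg) | down to 90 mg |

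Skipping levels does not help. After 0/3 at 20 and 40 mg (the history from which Table 15 scenario 2 goes straight to 90 mg), 1/3 at 90 mg gives P = 0.31 at 90 mg itself, and the model drops to 60 mg.

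**5. Varying the history.** Take every combination of 1 to 6 DLT-free patients at each lower level, then a first cohort of 1/3.

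- At 20, 40, 60 and 90 mg there are 1 + 6 + 36 + 216 = 259 histories, and 0 escalate. The lowest P at the next dose is 0.51, 0.30, 0.39 and 0.60 respectively. The 0.30 is at 60 mg after 0/6 at 20 mg and 1/3 at 40 mg.
- At 120 mg there are 6⁴ = 1,296 histories. P at 120 mg after 1/3 runs from 0.26 to 0.56, and the recomputed model moves down in all. Only about 15 of these histories would have made 120 mg admissible beforehand.
- On the 0/3 path, setting the prior correlation to −0.95, −0.8 or 0 leaves every next-dose P at 0.32 or more.

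**6. When escalation does occur.** If the 1/3 is a second cohort at 40 mg (1/6 in total, 0/3 at 20 mg), P at 60 mg is 0.22 and the model escalates. After 0/9 at 20 mg and 1/3 at 40 mg, P at 60 mg is 0.243 and it escalates. After 0/8 at 90 mg, 1/3 at 120 mg gives P = 0.248 and it stays. The 0/9 and 0/8 histories exceed the planned cohort range.

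**7. The 0-in-3 sentence.** It agrees with Table 15 scenarios 1 to 3. On the 0/3 path the recomputed model departs from it only from 90 mg up, where it stays because P at 120 mg is 0.39.

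**The case against.** **Wording and authority.** The paragraph opens with a general qualifier. The model is guidance, Section 20.1.1.3 is the rule, and the SRC decides. SAP Section 2 records that the study was terminated with two patients enrolled. All of this stands and limits the consequence. It does not make the sentence right: a general statement should describe the usual case, and in a usual first cohort the model never does what the sentence offers.

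**Intermediate doses.** The protocol allows added levels, and a small step up can pass. After 0/3 at 20 mg and 1/3 at 40 mg, 45 mg has P = 0.19 and a higher target probability than 40 mg (0.36 against 0.32). This is correct. But Section 7.1.1 and Section 20.1.1.1 use the word provisional for the listed doses, and escalation to the next listed dose is what fails.

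**First cohort.** The paragraph does not say that the 3 patients are the first at that dose, and 1/6 in total at 40 mg does lead to 60 mg. This stands, and the conclusion is limited to first cohorts accordingly.

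**Evidence for de-escalation.** Scenarios 5 to 9 start from 120 or 160 mg. On the histories shown, the recomputed model would not have admitted those doses (P before dosing 0.39 and 0.35 at 120 mg in scenarios 5 and 6; about 0.94 at 160 mg in scenario 7). At 20 to 90 mg, staying is the recommendation in roughly nine of ten of the 259 histories; the downward moves are all at 90 mg. So staying, which the paragraph lists, is the common answer at lower doses. The rows are still the protocol's own illustrations, and the paragraph summarising them omits what they show.

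**Accuracy of the grid.** The 0.03 gap in scenario 2 means that values near 0.25 (0.243, 0.248, and the 0.26 minimum at 120 mg) are not secure. The escalation result is: its smallest margin is 0.30 − 0.25 = 0.05, and on the 0/3 path 0.38 − 0.25 = 0.13.

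**Conclusion.** The concern holds. Under the stated prior and the 25% limit, 1 DLT in a first cohort of 3 at 20, 40, 60 or 90 mg does not permit escalation to the next planned dose in any of 259 histories within the planned cohort range. On the standard path the overdose probability there is 0.38 to 0.69, about one and a half to nearly three times the limit. The omission of de-escalation follows from the printed rows of Table 15 alone.

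The result assumes the planned dose levels, no DLTs at lower doses, and that the 3 patients are the first treated at that dose. It depends on the accumulated data, and a second cohort can lead to escalation. Nothing is claimed for 160 mg and above, which the limit bars before dosing. The paragraph alone does not set a dose. It should be corrected because it misstates, in the unsafe direction, what overdose control allows.

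**What to change.** Delete the closing paragraph of Appendix 2, or replace it with a short table of model recommendations by dose level and DLT count, generated from the Table 11 prior and the 25% limit. If text is kept, it should:

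- list de-escalation as a possible action after 1 DLT;
- allow escalation after 1 DLT only where the next dose meets the 25% limit;
- say that the recommendation depends on all data accumulated so far, including earlier patients at the same dose.

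The choice between deletion and replacement is for the sponsor and the SRC. The cost is one paragraph or a small table, with no change to the design, the prior or the rule.

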APPENDIX 4. GUIDELINES RELATED TO MDS CLASSIFICATION

Myelodysplastic Syndromes World Health Organization Classification System

Myelodysplastic Syndromes World Health Organization Classification System		
Category	Definition	
	Peripheral Blood Smear Evaluation	Bone Marrow Evaluation
Refractory cytopenia with unilineage dysplasia (RCUD): (refractory anemia [RA]; refractory neutropenia [RN]; refractory thrombocytopenia [RT])	Unicytopenia or bacytopenia ^a No or rare blasts (<1%) ^b	Unilineage dysplasia: ≥ 10% of the cells in one myeloid lineage < 5% blasts < 15% of erythroid precursors are ringed sideroblasts
Refractory anemia with ringed sideroblasts (RARS)	Anemia No blasts	≥ 15% of erythroid precursors are ringed sideroblasts Erythroid dysplasia only < 5% blasts
Refractory cytopenia with Multilineage dysplasia (RCMD)	Cytopenia(s) No or rare blasts (<1%) ^b No Auer rods < 1x10 ⁹ /L monocytes	Dysplasia in ≥ 10% of the cells in ≥ 2 myeloid lineages (neutrophil and/or erythroid precursors and/or megakaryocytes) < 5% blasts in marrow No Auer rods ± 15% ringed sideroblasts
Refractory anemia with excess blasts-1 (RAEB-1)	Cytopenia(s) < 5% blasts ^b No Auer rods < 1x10 ⁹ /L monocytes	Unilineage or multilineage dysplasia 5%-9% blasts ^b No Auer rods
Refractory anemia with excess blasts-2 (RAEB-2)	Cytopenia(s) 5%-19% blasts ^c Auer rods ^c < 1x10 ⁹ /L monocytes	Unilineage or multilineage dysplasia 10%-19% blasts ^c Auer rods ± ^c
Myelodysplastic syndrome - unclassified (MDS-U)	Cytopenias < 1% blasts ^b	Unequivocal dysplasia in < 10% of cells in one or more myeloid lineages when accompanied by a cytogenetic abnormality considered as presumptive evidence for a diagnosis of MDS ^d < 5% blasts
MDS associated with isolated del(5q)	Anemia Usually normal or increased platelet count No or rare blasts (<1%)	Normal to increased megakaryocytes with hypolobated nuclei < 5% blasts Isolated del(5q) cytogenetic abnormality No Auer rods

^a Bacytopenia may occasionally be observed. Cases with pancytopenia should be classified as MDS-U.

^b If the marrow myeloblast percentage is < 5% but there are 2% to 4% myeloblasts in the blood, the diagnostic classification is RAEB-1. Cases of RCUD and RCMD with 1% myeloblasts in the blood should be classified as MDS-U.

^c Cases with Auer rods and < 5% myeloblasts in the blood and less than 10% in the marrow should be classified as RAEB-2. Although the finding of 5% to 19% blasts in the blood is, in itself, diagnostic of RAEB-2, cases of RAEB-2 may have 5% blasts in the blood if they have Auer rods or 10% to 19% blasts in the marrow or both. Similarly, cases of RAEB-2 may have < 10% blasts in the marrow but may be diagnosed by the other 2 findings, Auer rods + and/or 5% to 19% blasts in the blood.

^d Includes unbalanced abnormalities -7 or del(7q), -5 or del(5q), i(17q) or t(17p), -13 or del(13q), del(11q), del(12p) or t(12p), del(9q), idic(X)(q13), balanced abnormalities t(11;16)(q23;p13.3), t(3;21)(q26.2;q22.1), t(1;3)(p36.3;q21.1), T2;11)(p21;q23),

inv(3)(q21q26.2), and t(6;9)(p23;q34), and complex karyotype (3 or more chromosomal abnormalities) involving one of more of the listed abnormalities.

Sources:

APPENDIX 5. CONTRACEPTIVE GUIDANCE AND COLLECTION OF PREGNANCY INFORMATION

Definitions:

Woman of Childbearing Potential (WOCBP)

A woman is considered fertile following menarche and until becoming post-menopausal unless permanently sterile (see below).

If fertility is unclear (eg, amenorrhea in adolescents or athletes) and a menstrual cycle cannot be confirmed before first dose of study intervention, additional evaluation should be considered.

Women in the following categories are not considered WOCBP

- Premenarchal
- Premenopausal female with 1 of the following:
 - Documented hysterectomy
 - Documented bilateral salpingectomy
 - Documented bilateral oophorectomy
- For individuals with permanent infertility due to an alternate medical cause other than the above, (eg, mullerian agenesis, androgen insensitivity), Investigator discretion should be applied to determining study entry.

Note: Documentation can come from the site personnel's review of the patient's medical records, medical examination, or medical history interview.
- Postmenopausal female
 - A postmenopausal state is defined as no menses for 12 months without an alternative medical cause.
 - A high follicle stimulating hormone level in the postmenopausal range may be used to confirm a postmenopausal state in women not using hormonal contraception or hormonal replacement therapy (HRT). However, in the absence of 12 months of amenorrhea, confirmation with more than one follicle stimulating hormone measurement is required.
 - Females on HRT and whose menopausal status is in doubt will be required to use one of the non-estrogen hormonal highly effective contraception methods if they wish to continue their HRT during the study. Otherwise, they must discontinue HRT to allow confirmation of postmenopausal status before study enrollment.

Contraception Guidance:

Female patients of childbearing potential (defined as first menarche through post-menopause or permanent sterilization) must agree to continued abstinence from heterosexual intercourse or 2 acceptable methods of birth control, including one highly effective method and one additional barrier method at the same time, during the study and for 7 months following the last dose of study drug.

Highly effective contraceptive methods are as follows:

- Combined (estrogen and progestogen containing) hormonal contraception associated with inhibition of ovulation:
 - Oral

- Intravaginal
- Transdermal
- Progestogen-only hormonal contraception associated with inhibition of ovulation:
 - Oral
 - Injectable
 - Implantable
- Intrauterine device
- Intrauterine hormone-releasing system
- Bilateral tubal occlusion

Additional barrier methods of contraception are as follows:

- Barrier methods of contraception (diaphragm, cervical cap, contraceptive sponge, male condom)

Note: Barrier methods have a higher failure rate than the highly effective methods listed above. To be considered acceptable, use two barrier methods (each partner must use one method) with a spermicide.
- Males must use the male condom (latex or other synthetic material) with spermicide
- Females must choose either a diaphragm with spermicide, or cervical cap with spermicide, or contraceptive sponge (spermicide is already in the contraceptive sponge)

Male patients (post-pubertal unless permanently sterilized by bilateral orchidectomy) must agree to use male contraception (condom) during the study and for 4 months following the last dose of study drug. Male patients must also not donate sperm during the Screening and treatment periods and for at least 4 months after the last dose of TP-0184.

Collection and Reporting Pregnancy Information

Any female patient who becomes pregnant while participating in the study will discontinue study intervention or be withdrawn from the study (see [Section 12.1.6.4.4](#)).

APPENDIX 6. INTERNATIONAL WORKING GROUP RESPONSE CRITERIA FOR MYELODYSPLASTIC SYNDROMES, 2006

Altering Natural History of MDS According to IWG Criteria for MDS (Cheson, 2006)	
Category	Response Criteria (responses must last at least 4 weeks)
Complete Remission (CR)	Bone marrow: $\leq 5\%$ myeloblasts with normal maturation of all cell lines ^a Persistent dysplasia will be noted ^{ab} Peripheral blood: 
- Hgb ≥ 11 g/dL- Platelets $\geq 100 \times 10^9/L$- Neutrophils $\geq 1.0 \times 10^9/L$ Blasts 0%
Partial Remission (PR)	All CR criteria if abnormal before treatment except: 
- Bone marrow blasts decreased by $\geq 50\%$ over pre-treatment but still $> 5\%$- Cellularity and morphology not relevant
Marrow CR ^a	Bone marrow: $\leq 5\%$ myeloblasts and decrease by $\geq 50\%$ over pre-treatment ^a Peripheral blood: if HI responses, they will be noted in addition to marrow CR ^a .
Stable Disease (SD)	Failure to achieve at least PR, but no evidence of progression for > 8 wks
Failure	Death during treatment or disease progression characterized by worsening of cytopenias, increase in percentage of bone marrow blasts, or progression to a more advanced MDS FAB subtype than pre-treatment.
Relapse After CR or PR	At least 1 of the following: 
- Return to pre-treatment bone marrow blast percentage- Decrement of $\geq 50\%$ from maximum remission/response levels in granulocytes or platelets- Reduction in Hgb concentration by ≥ 1.5 g/dL or transfusion dependence
Cytogenetic Response	Complete: 
- Disappearance of the chromosomal abnormality without appearance of new ones Partial: 
- At least 50% reduction of the chromosomal abnormality
Disease Progression	For subjects with: 
- Less than 5% blasts: $\geq 50\%$ increase in blasts to $> 5\%$ blasts- 5%-10% blasts: $\geq 50\%$ increase to $> 10\%$ blasts- 10%-20% blasts: $\geq 50\%$ increase to $> 20\%$ blasts- 20%-30% blasts^a: $\geq 50\%$ increase to $> 30\%$ blasts Any of the following: 
- $\geq 50\%$ decrease from maximum remission/response in granulocytes or platelets- Reduction in Hgb by ≥ 2 g/dL- Transfusion dependence
Survival	Endpoints: 
- Overall: death from any cause- Event free: failure or death from any cause- PFS: disease progression or death from MDS- DFS: time to relapse- Cause-specific death: death related to MDS

KEY: CR = complete remission; FAB = French-American-British; Hgb = hemoglobin; HI = hematologic improvement; IWG = International Working Group; MDS = myelodysplastic syndromes; PR = partial remission; PFS= progression-free survival; DFS= disease-free survival.

^a Dysplastic changes should consider the normal range of dysplastic changes (modification).

^b Modification to IWG (2000) response criteria.

Hematologic Improvement According to IWG Criteria (Cheson, 2006)	
Hematologic Improvement ^a	Response criteria (responses must last at least 8 week) ^b
Erythroid Response (HI-E) (pre-treatment, <11 g/dL)	
 - Hemoglobin increase by ≥ 1.5 g/dL - Relevant Reduction in units of RBC transfusions by an absolute number of at least 4 RBC transfusions/8 wk compared with the pretreatment transfusion number in the previous 8 wk
Platelet Response (HI-P) (pre-treatment, <100 X 10 ⁹ /L)	
 - Absolute increase of $\geq 30 \times 10^9$/L for subjects starting with $> 20 \times 10^9$/L platelets - Increase from $< 20 \times 10^9$/L to $> 20 \times 10^9$/L and by at least 100%^b
Neutrophil Response (HI-N) (pre-treatment, <1.0 X 10 ⁹ /L)	
 - At least 100% increase and an absolute increase $> 0.5 \times 10^9$/L^b
Progression or Relapse After HIC	
At least 1 of the following:
 
 - At least 50% decrease from maximum response levels in granulocytes or platelets - Reduction in Hgb by ≥ 1.5 g/dL - Transfusion dependence

KEY: HI-E = hematologic improvement erythroid response; HI-N = hematologic improvement neutrophil response; HI-P = hematologic improvement platelet response; IWG = International Working Group; RBC = red blood cell.

^a Pretreatment counts averages of at least 2 measurements (not influenced by transfusions, ie, no RBC transfusions for 2 weeks and no platelet transfusions for 1 week) ≥ 1 week apart (modification).

^b Modification to IWG (2000) response criteria.

^c In the absence of another explanation, such as acute infection, repeated courses of chemotherapy (modification), gastrointestinal bleeding, hemolysis, and so forth. It is recommended that the 2 kinds of erythroid and platelet responses be reported overall as well as by the individual response pattern.

Note: Deletions to the IWG response criteria are not shown. To convert hemoglobin levels from grams per deciliter to grams per liter, multiply grams per deciliter by 10.

Source: Cheson, BD, Greenberg PL, Bennett JM, Lowenberg B, Wijermans PW, Nimer SD, et al. Clinical application and proposal for modification of the International Working Group (IWG) response criteria in myelodysplasia. Blood 2006;108 (2):419-25.

